**Study hypotheses:** In acutely decompensated chronic heart failure patients who are admitted to the hospital due to symptoms and signs of congestion and who are not fully responsive to diuretic therapy, tailored, peripheral ultrafiltration complementary to low-dose diuretics provides better 90 day outcomes than usual care (guideline-directed medical therapy including IV diuretics).

Version: 5.0

- Patients:Acutely decompensated chronic heart failure patients who are
admitted to the hospital due to symptoms and signs of
congestion and who are not fully responsive to diuretic therapy
- Sample size: Sample size including 10% loss to follow-up and 13% treatment failure is 864 (432 in each group), minimum age of 18 years, no maximum age, both sexes, regions (western, central and eastern Europe).

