### (Modified) Intention-to-treat population (ITT=FAS)

Includes all subjects who were randomized and for whom complete efficacy data are available. We will analyze subjects lost to follow up based on subjects' status at time of withdrawal of consent and add a sensitivity analysis using multiple imputation for those with missing outcomes at 90 days.

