### Safety-population (SP)

Includes all subjects who were randomized.

Assignment of patients to analysis populations will be done during the data review meeting. Primary analysis will be based on the ITT population; an additional analysis on PP will be performed to assess validity of results. Safety analyses will be performed on the SP.

The primary endpoint measured at 90 days will be analyzed on an intention to treat basis. It is anticipated that there may be some "crossover" from the intervention group to the control group or from the control group to the intervention group. The number of crossovers will be documented to provide context for interpreting the primary results; however, treatment crossovers will be analyzed according to the intention to treat principle and thus will be included in the arm to which they were randomized.

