### **1.6.** SAMPLE SIZE JUSTIFICATION

Previously published results from clinical trials comparing intravenous loop diuretics to mechanical fluid removal by isolated veno-venous ultrafiltration have yielded conflicting results regarding heart failure-related rehospitalization. The present PURE-HF study is similar to the AVOID-HF (Costanzo et al., 2015) in terms of study design and targets. The primary objective of the AVOID-HF study was to determine whether UF prolonged the time to first HF event within 90 days of hospital discharge. Regarding sample size considerations, the AVOID-HF trial refers to different publications in order to provide an estimate of the combined HF event rate for the control group and the assumed reduction of the HF event rate in the UF group (Felker et al., 2011, O'Connor et al., 2011, Costanzo et al., 2007, Konstam et al., 2007, Hernandez et al., 2010, Ross et al., 2010).

Taking into account the assumptions and observations actually made in the prematurely terminated AVOID-HF study published by Costanzo et al. (Costanzo et al., 2016) we estimated that 864 patients (432 in each arm) should be sufficient to test whether there is a difference between the event proportions of the test and the control treatment. The proposed sample size calculations based on the two-sided Z test with unpooled variance and include the following assumptions: 1)  $\alpha$  of 0.05 ( $\alpha$ /2=0.025); 2) power (1- $\beta$ ) of 0.90; 3) an HF event rate for the loop diuretics group of 25% plus 2% cardiovascular death and 4) a reduction of the event proportion for the UF group of 37,5 % (this leads to an event proportion for the UF group of 16,88%). The estimated total sample size is displayed with additional patients included to account for 10% of subjects lost to follow-up and 13% treatment failures due to crossover during the treatment period

Event proportion			Sample size N		
control group	UF group	Reduction	Crude	Incl. 10% loss to FU	Incl. 10% loss to FU and 13% treatment failure
27.00%	16.88%	37.50%	694	764	864

- 1) Test for two proportions,
- 2) two-sided a of 0.05,
- 3) power of 0.90,
- 4) HF event rate of control group of 25% + 2% in-hospital death
- 5) an event proportion for the loop diuretics group (control group) of 27%,
- 6) an event proportion for the UF group (treatment group) of 16.88% (37.50% reduction),
- 7) including 10% loss to follow up and 13% crossover (i.e. treatment failure),

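### Section 1.6 allows for 13% crossover by adding patients at undiluted event rates, which is the wrong adjustment for an ITT primary analysis; the power at 864 should be restated on as-randomised proportions

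*Combined protocol and SAP*

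**What the plan says.** Section 1.6 sizes the trial with a two-sided unpooled Z test, alpha 0.05, power 0.90, and event proportions of 27% (control) and 16.88% (UF, a 37.5% reduction). The crude total is 694, rising to 764 for loss to follow-up and 864 for treatment failure; the text describes this as "additional patients included to account for 10% of subjects lost to follow-up and 13% treatment failures due to crossover during the treatment period". The table has one row, so the same two proportions stand behind all three totals. The numbered list under the table equates treatment failure with crossover: "including 10% loss to follow up and 13% crossover (i.e. treatment failure". The synopsis repeats the result: "Sample size including 10% loss to follow-up and 13% treatment failure is 864 (432 in each group".

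The origin of the inputs is given only in general terms: "Taking into account the assumptions and observations actually made in the prematurely terminated" earlier trial.

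Section 1.5 settles the analysis: "Primary analysis will be based on the ITT population". It expects crossover "from the intervention group to the control group or from the control group to the intervention group", and says that such patients "thus will be included in the arm to which they were randomized". For patients lost to follow-up, it uses their "status at time of withdrawal of consent and add a sensitivity analysis using multiple imputation", although the same definition also limits the population to patients with complete efficacy data.

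**The concern.** Loss to follow-up can remove patients from an analysis, so adding patients is a natural allowance for it. Crossover under ITT works differently. The patient still counts, in the arm of randomisation, but with an outcome shaped partly by the other treatment, so the difference between arms shrinks. Required sample size varies roughly with the inverse square of that difference, so a given percentage of dilution costs more than the same percentage of missing patients. Adding 13% at unchanged rates suits an analysis that drops crossovers, which is not the primary analysis here.

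At stake is the planning claim alone. A reader of section 1.6 takes 90% power for a 37.5% reduction as holding after crossover. If the result is neutral, it will be judged against that figure.

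**Working it through.** **Inputs from section 1.6:** p1 = 0.27; p2 = 0.27 x 0.625 = 0.16875 (printed as 16.88%); two-sided alpha 0.05; power 0.90; allowances of 10% and 13%; 432 per arm.

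**Step 1: reproduce the plan.** n per arm = (1.96 + 1.2816)^2 x [p1(1-p1) + p2(1-p2)] / (p1-p2)^2. With 0.27 and 0.1688 this is 346.2, so 347 per arm and 694 in total. Then 694 x 1.10 = 763.4, giving 764, and 764 x 1.13 = 863.3, giving 864. All three figures match, so crossover enters only as a head-count factor at undiluted rates.

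**Step 2: which analysis the factor fits.** Undoing both factors gives 864 / 1.10 / 1.13 = 695 patients, and power at 27% v 16.875% is 0.901. The 90% is therefore recovered if lost patients and crossovers are both left out.

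**Step 3: what x1.13 buys under ITT.** With variance roughly constant, multiplying N by 1.13 offsets a fall in the difference of 1 - 1/sqrt(1.13) = 5.9%. Losing 13% of the difference needs 1/0.87^2 = 1.32.

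**Step 4: power at 864 under ITT.** Let c and u be the shares of the control and UF arms that cross over, and k the share of the effect that a crossover loses (k = 1 means taking the other arm's full rate). Then:

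- control proportion = 0.27 - c x k x 0.10125
- UF proportion = 0.16875 + u x k x 0.10125
- power = Phi( difference / sqrt{[p1(1-p1) + p2(1-p2)] / n} - 1.96 )

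The documents give no values for c, u or k, so the rows below are assumed cases. Two values of n are used: 388.8 per arm (10% lost, 432 x 0.9) and 432 per arm (all contribute a full outcome).

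| Assumed case | ITT proportions | 10% lost | All contribute |
|---|---|---|---|
| No dilution, or 16.88% already as-randomised | 27.00 v 16.88% | 93.0% | 95.2% |
| 13% of UF arm, half loss | 27.00 v 17.53% | 89.1% | 92.0% |
| 13% of control arm, half loss | 26.34 v 16.88% | 89.8% | 92.6% |
| 13% of UF arm, full loss | 27.00 v 18.19% | 84.0% | 87.6% |
| 6.5% of each arm, full loss | 26.34 v 17.53% | 84.7% | 88.2% |
| 13% of control arm, full loss | 25.68 v 16.88% | 85.5% | 88.9% |
| 13% of each arm, full loss | 25.68 v 18.19% | 71.7% | 76.2% |

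Worked example (13% of UF arm, full loss, 10% lost): difference 0.0881; variance sum 0.27 x 0.73 + 0.1819 x 0.8181 = 0.3459; 0.0881 / sqrt(0.3459/388.8) = 2.953; 2.953 - 1.960 = 0.993; Phi(0.993) = 0.840.

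**Step 5: break-even.** 90% power survives only if crossover removes at most 5.2-6.1% of the 10.1-point difference with 10% lost, or 9.7-11.2% with all contributing. The lower end of each range applies when the loss falls in the UF arm, the upper end when it falls in the control arm.

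**Step 6: the status-at-withdrawal rule.** In the extreme case where all 10% lost count as non-events, both proportions are multiplied by 0.9 and n stays at 432. Power is then about 92.3% undiluted, 83-85% with 13% of one arm at full loss, and 70.5% with 13% of each arm at full loss. Each is about 1 point below the corresponding 10%-lost figure.

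**The case against.** The strongest reply is that no shortfall has been shown. The 37.5% reduction takes account of what an earlier trial assumed and observed. If it is that trial's as-randomised effect, crossover is already in it and 864 gives 93-95%. This stands: the documents do not say which kind of rate it is. But on that reading the 13% step has no purpose, so the section still needs correcting.

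Second, the added 100 patients do help under ITT, and crossover may cost only part of the effect, since the synopsis allows 1-7 UF sessions. Both points stand. With half loss in 13% of one arm the 90% claim roughly holds. With full loss in 13% of one arm it does not.

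Third, 72% or 76% needs 13% of each arm and complete loss of effect, which is a harsh case. It cannot be excluded, because the factor is applied to the total and section 1.5 expects crossover in both directions. It belongs as a sensitivity case, not as the headline.

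Fourth, crossovers will be documented and a per-protocol analysis is planned. That helps interpretation but does not repair the power statement.

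A reader might go further and infer that the trial is underpowered, that 864 is miscalculated, or that more patients are needed. The documents support none of these. The arithmetic reproduces exactly, and any shortfall depends on the direction and share of crossover, the effect lost, and the type of rate, none of which is stated.

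**Conclusion.** The concern holds as a mismatch between the stated adjustment and the stated analysis. This is more than missing detail: a head-count factor at undiluted rates does not protect an ITT comparison against 13% dilution. Confidence in the mismatch is high, because both the factor and the ITT rule are explicit.

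The size is conditional. If 27% and 16.88% are full-treatment rates and crossovers lose the whole effect, the central case of 13% of one arm (or 6.5% of each) gives a power some 4 to 6 points below 90% with 10% lost, and 1 to 2 points below with all contributing. The range across the other assumptions runs from about 72% to 95%, or about 1 point lower at the bottom if lost patients count as non-events. It should be fixed, but the validity of the planned analysis is not affected.

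**What to change.** Keep 864 and its derivation (694, 764, 864). In section 1.6:

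1. Label the power of 0.90, in assumption 2 of the text and item 3 of the list, as the power of the crude 694 at undiluted rates. Otherwise the section would carry two competing power claims.
2. State whether 16.88% is a full-treatment or an as-randomised rate.
3. State the crossover share assumed in each arm and the share of effect that a crossover is taken to lose.
4. Give the resulting ITT event proportions.
5. Report the power at 864 on those proportions, led by the case of 13% of one arm, with 13% of each arm as a sensitivity case. If 16.88% is as-randomised, say so, report 93% / 95%, and note that the crossover allowance is not needed.
6. Compute that power under the loss-to-follow-up rule of section 1.5. Since that section mentions both complete efficacy data and status at withdrawal, say which one the calculation uses.

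The cost is two reworded lines and a short added paragraph. The table and the synopsis sentence stay true. No extra patients are needed, and alpha, endpoint and analysis do not change. The downside is that the stated power becomes conditional and possibly lower.

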### **1.7.** INTERIM ANALYSIS

No formal interim analysis will be performed. The requirements for safety are further defined in the context of the DMC and detailed in the DMC charter. Decisions will be

based on e.g. inspection of study-database, AE listings, event rates, etc. Thus, a statistical interim analysis is not applicable.
